5.2 Ethical Conduct of the Study

This study will be conducted in accordance with the Note for Guidance on GCP (ICH Harmonized Tripartite Guideline E6 (R1); FDA CFR [21 CFR § 50, 56, 312]), Declaration of Helsinki (Fortaleza, Brazil, October 2013; [Appendix 18.1](#)), and all applicable regulatory requirements.

5.3 Subject Information and Consent

The Investigator will explain the benefits and risks of participation in the study to each subject and obtain written informed consent. Written informed consent must be obtained prior to the subject entering the study and before initiation of any study-related procedure (including administration of study drug).

The Sponsor will provide a sample informed consent form, based on the elements of informed consent in [Appendix 18.2](#). The final, version dated form must be agreed to by the Sponsor and the IRB and will contain all elements in the sample form, in language readily understood by the subject. Each subject's original consent form, personally signed and dated by the subject and by the person who conducted the informed consent discussion, will be retained by the Investigator. The Investigator will supply all enrolled subjects with a copy of their signed informed consent.

The consent form may need to be revised during the study should important new information become available that may be relevant to the safety of the subject. In this instance approval should always be given by the IRB. Subjects on treatment should be informed of the changes and re-consented if the consent was updated for safety reasons. This is documented in the same way as previously described.

6. INVESTIGATORS AND STUDY ADMINISTRATIVE STRUCTURE

The study will be performed at approximately 35 sites in North America.

Monitoring and Evaluation Committee(s):

The Phase 1 Portion of this study is an open-label, dose-escalation study. Safety will be monitored through the surveillance of adverse events (AEs), laboratory test measures, physical examination findings, and concomitant medication records and will be monitored in an ongoing process as part of the dose-escalation portion of this study by a Safety Monitoring Committee (SMC). During the Phase 2 Portion, an Independent Data Monitoring Committee (IDMC) will also periodically assess the ongoing safety data and make recommendations to either continue evaluating the combination or to stop the study due to toxicity concerns. Conditions requiring IDMC action are provided in [Section 13.6.10](#).

Clinical Laboratories:

Central clinical laboratory services will be provided by a central laboratory (refer to the study manual) for protocol-required hematology and serum chemistry tests; central laboratory results will not be provided to the Investigator. Additional analyses of clinical laboratory samples may be conducted by certified local laboratories. Documentation of certification will be filed with study documentation.

Analyses of antibody-drug conjugate (ADC; vadastuximab talirine) and SGD-1882 concentrations and other research studies will be performed at central facilities that will be identified in the study manual.

Clinical Research Organization (CRO):

PRA Health Sciences
[name]
[name]

Medical Monitor/Medical Expert:

[REDACTED]

7. INTRODUCTION

7.1 Disease Review

The myelodysplastic syndromes (MDS) represent a group of heterogeneous hematopoietic disorders derived from an abnormal multipotent progenitor cell. They are characterized by ineffective hematopoiesis, bone marrow failure, peripheral blood cytopenias, and reduced survival. MDS may be classified as indolent or aggressive (lower- or higher-risk), depending on life expectancy and likelihood of progression to acute myeloid leukemia (AML). The annual age-adjusted incidence of MDS is approximately 4.5 per 100,000 in the US. MDS is associated with age, and the incidence of MDS for Americans ≥ 50 years of age is approximately 15.5 per 100,000 per year. [1]

Prognosis in MDS depends on the number of bone marrow blasts, cytogenetic abnormalities, and the amount of peripheral blood cytopenias. These risk factors are scored in the International Prognostic Scoring System (IPSS) as percent bone marrow blasts ($<5\%$ =0, 5% - 10% =0.5, and 11% - 20% =1.5), karyotype (good [normal, -Y, del(5q), del(20q)] =0; intermediate [other abnormalities] =0.5, and poor [≥ 3 abnormalities] =1.0), and cytopenias (0 or 1 =0 and 2 or 3 =0.5). Patients are assigned scores based on the sum of risk factor scores, and prognosis is defined as Low (score =0), Intermediate-1 (score =0.5-1.0), Intermediate-2 (score =1.5-2.0), and High (score ≥ 2.5) risk. These scores have been shown to predict survival and risk of progression to AML. [2; Appendix 18.5.1] MDS can also be classified according to the World Health Organization (WHO) system using morphologic, cytochemical, and immunophenotypic features of the neoplastic cells, [Appendix 18.5.2] an update to the older French-American-British (FAB) classification.

[figure not shown]
For patients with Low or Intermediate-1 risk MDS, standard treatment is usually supportive care; symptomatic anemia is treated with growth factors as appropriate (patients with del(5q) and symptomatic anemia are generally treated with lenalidomide). Among patients who are intolerant or fail to respond to treatment with erythropoiesis-stimulating agents, those with low serum erythropoietin levels (<500 mU/mL) may be candidates for immunosuppressive therapy (IST) with antithymocyte globulin/cyclosporine. Those not candidates for IST and those who are intolerant or fail to respond to IST are generally treated with hypomethylating agents (HMAs; azacitidine or decitabine); HMA treatment generally continues for at least 4-6 cycles with maintenance treatment until disease progression. [3]

For patients with Intermediate-2 or High risk MDS, allogeneic hematopoietic stem cell transplant (allo-HCT) is the preferred treatment for patients who are candidates and have a donor stem cell source available. However, the majority of higher-risk MDS patients are not eligible for allo-HCT due to age, comorbidities, or donor availability. For such patients who are not candidates for allo-HCT, treatment with HMAs as described above is appropriate. In this setting, azacitidine is the preferred agent, as only azacitidine has demonstrated an improvement in overall survival (OS) when compared to standard of care in a randomized controlled trial. [4] There is no standard treatment for patients who do not respond to or relapse following HMA treatment. [3]

CD33 is an important cell-surface marker that is found on cells committed to the myeloid lineage, myeloid leukemic blasts, and mature monocytes, but not on normal pluripotent hematopoietic stem cells. [5, 6] CD33 has been used to diagnose AML, [7] and anti-CD33 antibodies have been investigated as therapy in AML. [8, 9] Though lasting clinical benefit has not been demonstrated with gemtuzumab ozogamicin, CD33 continues to be a target of interest in AML. [9, 10] In MDS, CD33 is also highly expressed in myeloid blast cells, as well as myeloid-derived suppressor cells (MDSC), which have been shown to mediate myelodysplasia via suppressive cytokine production and enhanced apoptosis. [6, 11, 12]

7.2 Compound Review

Vadastuximab talirine (also referred to as SGN-CD33A or 33A) is an ADC composed of an antibody (h2H12ec) conjugated to a DNA-cross linking pyrrolobenzodiazepine (PBD) dimer drug (SGD-1882) via a protease-cleavable linker. The antibody targets the antigen CD33, which is expressed on leukemic cells of myeloid origin such as on AML, chronic myeloid leukemia, and MDS cells. In nonclinical studies, vadastuximab talirine was active in animal models of AML, including in multidrug-resistant lineages. [13]

There are 2 ongoing clinical studies with vadastuximab talirine. The first-in-human phase 1 clinical trial (Study SGN33A-001) is a dose-escalation study to evaluate the safety and tolerability of vadastuximab talirine in subjects with CD33-positive AML. Dosing began at 5 mcg/kg on Day 1 (in repeated 3-week cycles) and has been escalated to 60 mcg/kg. An additional arm was added to study vadastuximab talirine in combination with HMAs in subjects with CD33-positive AML, which began dosing at 10 mcg/kg (in repeated 4-week cycles). As of this writing, 86 subjects with AML had received monotherapy and 21 subjects had received vadastuximab talirine plus HMA combination therapy in Study SGN33A-001. The most common AEs in the monotherapy cohorts were febrile neutropenia (70%), fatigue (45%), anemia (26%), decreased appetite (26%), dyspnea (26%), thrombocytopenia (24%), constipation (23%), nausea (23%), cough (22%), diarrhea (22%), and peripheral edema (21%). The most common AEs observed in the combination cohort of SGN33A-001 were fatigue (38%), febrile neutropenia (38%), constipation (19%), and nausea (19%). [14]

The phase 1b clinical trial (Study SGN33A-002) is a dose-escalation study to evaluate the safety and tolerability of vadastuximab talirine in combination with standard induction and consolidation therapy and as maintenance monotherapy in subjects with newly diagnosed AML. Study SGN33A-002 began dosing at 10 mcg/kg for induction (Days 1 and 4) and consolidation (Day 1 of 28-day cycles for up to 4 cycles), and 5 mcg/kg for maintenance (Day 1 of 6-week cycles). As of this writing, 7 subjects with AML had enrolled in Study SGN33A-002. Adverse events observed in SGN33A-002 were febrile neutropenia, headache, hyperglycemia, and stomatitis (1 subject each). Additional clinical data are presented in the Investigator's Brochure. [14]

Azacitidine (VIDAZA®) is a nucleoside metabolic inhibitor that is indicated for the treatment of subjects with certain FAB MDS subtypes. [15] Azacitidine is a pyrimidine nucleoside analog of cytidine. It is believed to exert its anti-neoplastic effects by causing hypomethylation of DNA and direct cytotoxicity on abnormal hematopoietic cells in the bone marrow. Azacitidine is indicated for refractory anemia (RA) or RA with ringed sideroblasts (if accompanied by neutropenia or thrombocytopenia or requiring transfusions), RA with excess blasts (RAEB), RA with excess blasts in transformation (RAEB-T), and chronic myelomonocytic leukemia MDS subtypes. Azacitidine is administered at a dose of 75 mg/m² subcutaneously (SC) or intravenously (IV), daily for 7 days every 28 days. [15] At some institutions, azacitidine is administered on a 5 days on/2 days off/2 days on schedule, rather than for 7 consecutive days. [3, 16 – 18]

7.3 Clinical Study Rationale

Though HMAs are part of the standard treatment protocols for MDS, the benefits are limited. In subjects with Intermediate-2 or High risk MDS, median OS with azacitidine was 21 to 24 months. [19, 20] Decitabine has been shown to produce durable responses, but an improvement in OS has not been demonstrated. [21] Improved treatment options are needed for Intermediate-2 and High risk MDS, particularly for subjects not eligible for allo-HCT. By targeting CD33, combining vadastuximab talirine with azacitidine may add significant activity in allo-HCT-ineligible subjects compared to treatment with azacitidine alone. Vadastuximab talirine (10 mcg/kg) has been administered with azacitidine at standard doses (75 mg/m² per day for 7 consecutive days) to subjects with AML without unacceptable toxicity in Study SGN33A-001, suggesting that the combination may also have an acceptable safety profile in subjects with MDS.

The study will assess the safety of vadastuximab talirine in combination with azacitidine in a dose-escalation Phase 1 Portion of the study and its efficacy in a double-blind Phase 2 Portion at the dose identified in phase 1. The safety of this drug combination will be monitored in an ongoing process as part of the dose-escalation portion of this study by an SMC, and safety and toxicity will be monitored during the double-blind portion by an IDMC.

8. STUDY OBJECTIVES

8.1 Primary Study Objective

8.1.1 Phase 1 Portion

- To determine the recommended vadastuximab talirine (SGN-CD33A) dose in combination with azacitidine.

8.1.2 Phase 2 Portion

- To compare the overall response rate (ORR = complete response + partial response [CR+PR]) between treatment arms.

8.2 Secondary Study Objectives

- To evaluate the safety of the combination of vadastuximab talirine and azacitidine (Phase 1 and Phase 2 Portions)
- To compare the CR rate between treatment arms (Phase 2 Portion)
- To compare the hematologic improvement (HI) rate between treatment arms (Phase 2 Portion)
- To compare the duration of response (DOR) between treatment arms (Phase 2 Portion)
- To compare progression-free survival (PFS) between treatment arms (Phase 2 Portion)
- To compare the rate of transformation to AML between treatment arms (Phase 2 Portion)
- To compare the OS between treatment arms (Phase 2 Portion)

8.3 Exploratory Objectives

- To assess the pharmacokinetics (PK) and pharmacodynamics of vadastuximab talirine (Phase 1 and Phase 2 Portions)
- To assess the incidence of antitherapeutic antibodies (ATAs) against vadastuximab talirine (Phase 1 and Phase 2 Portions)
- To assess exploratory biomarkers of clinical activity of vadastuximab talirine in combination with azacitidine (Phase 1 and Phase 2 Portions)
- To assess quality of life (QoL; Phase 2 Portion)

8.4 Endpoints

8.4.1 Primary Endpoint

The primary endpoint of the Phase 1 Portion of the study is to determine the recommended dose for the Phase 2 Portion, based upon the maximum tolerated dose (MTD).

The primary efficacy endpoint of the Phase 2 Portion of the study is the ORR, defined as the proportion of subjects who achieve any category of CR (CR and Marrow CR) or PR based on the 2006 International Working Group (IWG) criteria for MDS. [22]

8.4.2 Secondary Efficacy Endpoints

Secondary efficacy endpoints of the Phase 2 Portion of the study are the following:

- CR rate
- HI rate
- DOR
- PFS
- Rate of transformation to AML
- OS

8.4.3 Pharmacokinetic and Antitherapeutic Antibody Assessments

- Estimates of selected PK parameters for plasma vadastuximab talirine and released SGD-1882
- Incidence of ATA

8.4.4 Biomarker Assessments

Biomarker assessments may include

- CD33 expression level
- Abundance of MDSC
- Characterization of leukocyte subpopulations in peripheral blood (peripheral blood mononuclear cells; PBMCs)
- Variation in sequence of CD33 and genes commonly mutated in MDS and hematologic malignancies

- Soluble CD33
- Abundance of a variety of cytokines
- Testing for Paroxysmal Nocturnal Hemoglobinuria (PNH) and human leukocyte antigen (HLA)-DR15

8.4.5 Safety Criteria

Safety assessments will consist of the surveillance of AEs, laboratory test measures, physical examination findings, and concomitant medication records.

8.4.6 Quality of Life

Quality of life will be assessed with the Quality of Life Questionnaire (QLQ)-C30 patient reported outcomes (PRO) tool at protocol-defined time points.

9. INVESTIGATIONAL PLAN

9.1 Overall Study Design and Plan

This is a phase 1/2 study to evaluate the combination of vadastuximab talirine (SGN-CD33A) and azacitidine in subjects with previously untreated IPSS Intermediate-2 or High risk MDS. In the Phase 1 Portion of the trial, escalating doses of vadastuximab talirine will be evaluated in combination with azacitidine, and 1 dose will be selected for the randomized, double-blind, placebo-controlled Phase 2 Portion of the study, which is designed to compare the ORR between the 2 study arms.

[figure not shown]
9.1.1 Phase 1 Portion – Open-Label Dose Evaluation

Cohorts of 6 dose-limiting toxicity (DLT)-evaluable subjects will be enrolled in an open-label fashion to receive vadastuximab talirine in combination with azacitidine in 28-day cycles, starting at 5 mcg/kg vadastuximab talirine. The DLT-evaluable population will include all Phase 1 subjects who have completed at least Cycle 1 of treatment (Cycle 1 of treatment is completed when the patient receives the first dose of azacitidine on Day 1 of Cycle 2) *or* discontinued study treatment because of AEs, or for a safety-related reason before having had the opportunity to receive the first dose of azacitidine on Day 1 of Cycle 2. In the Phase 1 Portion of the study, DLTs will be defined as posttreatment grade 4 neutropenia or grade 4 thrombocytopenia lasting >42 days from the start of therapy, in the absence of evidence of active MDS, or any grade 3 or higher non-hematologic toxicity that is clearly NOT resulting from underlying MDS or azacitidine, with the exception of:

- a. Grade 3 allergic reaction, fatigue, asthenia, anorexia, or constipation
- b. Grade 3 nausea, vomiting, or diarrhea not requiring tube feeding or total parenteral nutrition or hospitalization
- c. Febrile neutropenia (which resolves with appropriate treatment or marrow recovery), infection, bleeding, or other expected direct complications of cytopenias due to active MDS

If 2 or more subjects in a 6-subject cohort have DLTs, that dose level will be considered to have exceeded the MTD. If 5 mcg/kg vadastuximab talirine in combination with azacitidine is considered tolerable (≤ 1 of 6 subjects experiences a DLT), a cohort of 6 DLT-evaluable subjects will receive 10 mcg/kg vadastuximab talirine and azacitidine. If 10 mcg/kg vadastuximab talirine in combination with azacitidine is considered tolerable, a cohort of 6 DLT-evaluable subjects will receive 15 mcg/kg, and if 15 mcg/kg vadastuximab talirine in combination with azacitidine is considered tolerable, a cohort of 6 DLT-evaluable subjects will receive 20 mcg/kg. If 5 mcg/kg vadastuximab talirine in combination with azacitidine is not considered tolerable (> 1 of 6 subjects experiences a DLT), a cohort of 6 DLT-evaluable subjects will receive 3 mcg/kg vadastuximab talirine and azacitidine. The dose-escalation plan is presented in [Figure 1](#).

Figure 1: Study Schematic – Phase 1 Portion

DLT = dose-limiting toxicity; MTD = maximum tolerated dose.

Azacitidine will be given on 7 days per cycle, either on the first 7 days or 5 days on/2 days off/2 days on; vadastuximab talirine will be given after azacitidine on the last day of azacitidine administration in each cycle. Response assessments (bone marrow examination and complete blood count [CBC]) will be conducted on Day 22-29 of even-numbered cycles until CR, then every 4 cycles thereafter. Subjects may continue on study treatment until disease progression, relapse, or unacceptable toxicity. After discontinuation of study treatment, subjects who have not experienced progression or relapse will continue to be assessed for response every 4 months through 24 months after the end of treatment (EOT) or until initiation of another anticancer treatment, progression, or relapse, whichever comes first. All subjects will be contacted for survival status every 2 months after EOT in follow-up until death or study closure, whichever comes first. Safety will be monitored through the surveillance of AEs, laboratory test measures, physical examination findings, and concomitant medication records. An additional bone marrow examination will be conducted for research purposes for subjects in the Phase 1 Portion of the study only.

After 6 DLT-evaluable subjects have had the opportunity to complete at least Cycle 1 (Cycle 1 of treatment is completed when the patient receives the first dose of azacitidine on Day 1 of Cycle 2) of treatment in each planned dose cohort, the data will be aggregated and analyzed by an SMC (Section 13.6.9). Based on the evaluation of the data, including the incidence of DLT in each cohort, the SMC may recommend the dose of vadastuximab talirine for the Phase 2 Portion of the study at the time of the evaluation. If additional safety information is required to recommend a phase 2 dose, the SMC could recommend enrollment of up to 12 additional treated subjects to continue to evaluate the safety of the combination at vadastuximab talirine dose(s) of 3, 5, 10, or 20 mcg/kg. Subsequently, upon completion of dose escalation, up to 12 more expansion patients may be enrolled (maximum of 24 expansion patients total), at any dose level not previously shown to exceed the MTD, to further characterize safety, PK, and activity.

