Hospitalization:	The AE required or prolonged an existing inpatient hospitalization. Hospitalizations for elective medical or surgical procedures or treatments planned before the signing of informed consent in the study or routine check-ups are not serious AEs by this criterion. Admission to a palliative unit or hospice care facility is not considered to be a hospitalization. Hospitalizations or prolonged hospitalizations for scheduled therapy of the underlying cancer or study target disease need not be captured as SAEs.
Disabling/ incapacitating:	Resulted in a persistent or significant incapacity or substantial disruption of the patient's ability to conduct normal life functions.
Congenital anomaly or birth defect:	An adverse outcome in a child or fetus of a patient exposed to the molecule or study treatment regimen before conception or during pregnancy.
Medically significant:	The AE did not meet any of the above criteria, but could have jeopardized the patient and might have required medical or surgical intervention to prevent one of the outcomes listed above or involves suspected transmission via a medicinal product of an infectious agent.

Adverse Event Severity

AE severity should be graded using the NCI CTCAE, version 4.03 ([Appendix 18.4](#)). These criteria are provided in the study manual.

AE severity and seriousness are assessed independently. 'Severity' characterizes the intensity of an AE. 'Serious' is a regulatory definition and serves as a guide to the Sponsor for defining regulatory reporting obligations (see definition for SAEs).

Relationship of the Adverse Event to Study Treatment

The relationship of each AE to each study drug (vadastuximab talirine or azacitidine) should be evaluated by the Investigator using the following criteria:

Related:	There is evidence to suggest a causal relationship between the drug and the AE, such as: 
An event that is uncommon and known to be strongly associated with drug exposure (eg, angioedema, hepatic injury, Stevens-Johnson Syndrome)An event that is not commonly associated with drug exposure, but is otherwise uncommon in the population exposed to the drug (eg, tendon rupture)

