13.2 Sample Size Estimation

Phase 1 Portion (minimum of 6 subjects per cohort): Six subjects are adequate to appropriately assess the safety profiles and DLT rates of differing dose levels of vadastuximab talirine in combination with azacitidine. If the true incidence rate of DLT is 10%, the probability of considering a dose level tolerable (ie, ≤ 1 of 6 subjects experiences a DLT) will be 88.6%. If the true incidence rate of DLT is 50%, the probability of considering a dose level tolerable will be 10.9%.

Phase 2 Portion (106 subjects): A sample size of 106 subjects will provide 85% power to detect a treatment difference in ORR, assuming an ORR of 30% for azacitidine alone vs 55% for the combination of vadastuximab talirine with azacitidine, at a 2-sided 0.1 alpha level.

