Section: 12.1.3, Reporting Periods for Adverse Events and Serious Adverse Events, page 72

Delete:

~~... Ongoing non-serious AEs of interest (including, but not limited to, neuropathy) may be followed until resolution, return to baseline, or study closure.~~

Section: 12.1.5, Sponsor Safety Reporting Requirements in the United States, page 73

Change:

~~In this study, the SAEs that do not require individual IND safety reports are disease progression events.~~ **In this study SAEs of leukemic relapse do not require individual IND safety reports. Events of febrile neutropenia are anticipated in this population and individual IND safety reports will not be submitted to the FDA.** These anticipated SAEs will be...

Section: 13.5.4, Modified Intent-to-Treat, page 75

Change (section title):

13.5.4 ~~Efficacy Evaluable~~ **Efficacy Evaluable Modified Intent-to-Treat** Population

Change:

The ~~efficacy evaluable~~ **modified intent-to-treat (mITT)** population will include all ITT subjects who received at least 1 dose of study medication (azacitidine or vadastuximab talirine).

Section: 13.6.3, Subject Disposition, page 76

Add:

The number and percent of subjects who discontinue treatment **and withdraw from study** and the reasons for discontinuation **or withdrawal** will be summarized.

Section: 13.6.4.2, Secondary Efficacy Endpoints, page 76

Change:

CR rate will be summarized with ~~95%~~**90%** confidence intervals.

Section: 13.6.8, Additional Data, page 78

Delete:

~~All data collected on the eCRFs will be included in data listings.~~

Section: Global

Replace:

Version ~~01~~, Date ~~24 September 2015~~

With:

Version **02**, Date **18 May 2016**

18.9 Appendix 9: Summary of Changes in Version 3

RATIONALE:

The protocol was amended to

- Clarify the DLT definition (excluding AEs clearly related to azacitidine, and removing the requirement of attribution as related to study treatment from DLT definition)
- Exclude subjects who are candidates for stem cell transplant from the study and to explicitly require a minimum of 30 days between the last dose of vadastuximab talirine and stem cell transplant for those subjects who become candidates during the study
- Add hepatic SAEs (including sinusoidal obstruction syndrome/veno-occlusive disease [SOS/VOD]) as adverse events of special interest
- Add requirements for action by the Independent Data Monitoring Committee (IDMC) to make recommendations based on the occurrence of SOS/VOD

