### 7.1 Safety Monitoring Committee

During the Phase 1 Portion of the study, the SMC will monitor the trial for safety and dose limiting toxicities (DLTs). Each dose cohort will be evaluated for DLTs prior to enrolling the subsequent cohort. Sufficient trends in safety or toxicity identified by the SMC may result in

enrollment suspension or study termination, as recommended by the SMC. The SMC may also recommend predetermined or intermediate dose levels for dose escalation and/or expansion for the Phase 2 portion of the study based on review of safety and efficacy data. In the event of a death or emergence of a life-threatening acute or chronic toxicity within the safety reporting period, enrollment to the study will be temporarily halted until the SMC convenes to review the aggregate safety data to determine if enrollment will resume, and the appropriate dose level moving forward. Additionally, the investigators and the PRA Medical Monitor will meet regularly (via teleconference, see [section 7](#)) to assess safety on an ongoing basis.

Meetings will be held approximately 1 week after the last patient completes the DLT period. The DLT period is defined as the time from start of study therapy in Cycle 1 through the start of day 1 of Azacitidine during Cycle 2, or the time at which a patient discontinues treatment due to study treatment-related toxicity prior to receiving Day 1 Cycle 2 treatment. This will occur for each dose escalation cohort that has been initiated and on an ad hoc basis as needed based on emerging safety data.

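### As written, a grade 3+ non-hematologic event of uncertain cause is not a DLT, so the rule of at most 1 DLT in 6 can under-count toxicity by an amount the documents do not allow us to size

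*Protocol*

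**What the plan says.** The definition appears with the same wording in the Protocol Synopsis, Protocol 9.1.1 and SAP 3.1.1. It has two limbs. The hematologic limb covers prolonged grade 4 neutropenia or thrombocytopenia and has its own test, based on the absence of active MDS. The non-hematologic limb is "any grade 3 or higher non-hematologic toxicity that is clearly NOT resulting from underlying MDS or azacitidine", followed by exceptions a to c.

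The count feeds a fixed rule: "If 2 or more subjects in a 6-subject cohort have DLTs, that dose level will be considered to have exceeded the MTD". SAP 7.1 adds: "Each dose cohort will be evaluated for DLTs prior to enrolling the subsequent cohort". Protocol 8.4.1 bases the Phase 2 dose on the MTD.

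Protocol 13.2 and SAP 3.2 give the chance that a six-subject cohort is declared tolerable: 88.6% at a true DLT rate of 10%, and 10.9% at 50%.

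On causality, Protocol 12.1.1 says: "The relationship of each AE to each study drug (vadastuximab talirine or azacitidine) should be evaluated by the Investigator". The only levels are Related and Unrelated.

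The rationale in Protocol Appendix 9 (changes in Version 3) describes the purpose of the DLT edit as "excluding AEs clearly related to azacitidine, and removing the requirement of attribution as related to study treatment from DLT definition".

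**The concern.** The sentence makes an event countable only once MDS and azacitidine have both been clearly ruled out. If either remains possible, the event is not a DLT. No current section gives a separate rule for uncertain cause.

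Such uncertainty is built into the design. Eligibility requires Intermediate-2 or High risk MDS (Protocol 9.4.1), and vadastuximab talirine follows azacitidine on the last azacitidine day of the cycle (Protocol 9.1.1). Both alternative explanations are therefore present for every subject when the first investigational dose is given.

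What is at stake is the decision to escalate and the Phase 2 dose. If some toxicity never enters the count, a dose can pass the 1-of-6 rule more often than the stated probabilities suggest. A second risk is inconsistency: sites and SMC members could classify the same kind of event differently from one cohort to the next.

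**Working it through.** **1. The two defaults side by side**

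| Source | Rule on azacitidine as a cause | Event of uncertain cause |
|---|---|---|
| Synopsis, Protocol 9.1.1, SAP 3.1.1 | count only if clearly not due to it | not counted |
| Appendix 9 rationale | leave out if clearly due to it | counted |

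The two agree when the cause is clear and differ when it is not. The Related/Unrelated scale does not settle the matter. It has no level equivalent to *clearly NOT*, and no section says how the two map.

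**2. The plan's own figures**

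Inputs: n = 6, and tolerable means at most 1 DLT (Protocol 9.1.1, 13.2).

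P(tolerable) = (1 − p)^6 + 6p(1 − p)^5

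- p = 0.10: 0.5314 + 0.3543 = 0.8857, matching 88.6%.
- p = 0.50: 0.0156 + 0.0938 = 0.1094, matching 10.9%.

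**3. Effect of partial counting**

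Let c be the share of subjects with DLT-type toxicity, of either limb, who are counted. The documents do not give c, so the values below are assumptions. The counted rate is p × c, put into the same formula.

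| True rate p | c = 1 | c = 0.90 | c = 0.75 | c = 0.50 |
|---|---|---|---|---|
| 10% | 88.6% | 90.5% | 93.1% | 96.7% |
| 33.3% | 35.1% | 42.0% | 53.4% | 73.7% |
| 50% | 10.9% | 16.4% | 27.4% | 53.4% |

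For the bottom row, the counted rates are 0.50, 0.45, 0.375 and 0.25.

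**4. What each c implies**

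The wording touches only the non-hematologic limb. If s is the share of DLTs that are non-hematologic and m is the share of those missed, c = 1 − s × m.

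- s = 0.5, m = 0.2: c = 0.90.
- s = 0.5, m = 0.5: c = 0.75.
- c = 0.50 needs s × m = 0.5, for example all DLTs non-hematologic and half of them missed.

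The 53.4% figure is therefore the far end of this range and should not be read as a central estimate.

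**The case against.** The strongest reply has five parts.

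*The text is consistent.* All three places agree, and the itemised edit in Appendix 9 matches them. A summary of changes that differs from current text is not an error. This stands. A reader might infer that the protocol contradicts itself here, but the rationale is only evidence of what the drafters meant.

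*The stated probabilities are right.* They condition on the rate of DLT as defined ("If the true incidence rate of DLT is 10%, the probability of considering a dose level tolerable" is given as 88.6%). This also stands. A reader might infer that 88.6% and 10.9% are wrong, but both reproduce.

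*The under-count is not established.* A reader might infer that every uncertain event will be dropped and that cohorts will in fact escalate on under-counted toxicity. The documents do not show that. Investigators make a forced two-way judgement per drug, its mapping to the definition is unstated, and sites or the SMC may apply the intent in the rationale. What stands is a risk created by the written rule.

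*There are safeguards.* The SMC analyses aggregate data, of which DLT incidence is only a part (Protocol 9.1.1). It can recommend suspending enrollment on safety trends, and a death or life-threatening toxicity halts enrollment until it has met (SAP 7.1). Grade 3–5 events are tabulated by dose level and by relationship to each drug (SAP 9.6.1.2). These measures help, mainly for the most severe events. They do not change the DLT count, and they do not isolate non-life-threatening grade 3 events left out for uncertain cause.

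*A narrow default has a reason.* Counting background events would stop acceptable doses. If p = 10% and, as an assumption, an independent 10% of subjects have a background event that is counted, the counted rate is 1 − 0.9 × 0.9 = 19%, and the chance of passing falls from 88.6% to 68.0%. This is why the choice of default is a clinical one, to be made openly.

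**Conclusion.** The point holds as a risk in the non-hematologic limb of the DLT definition. On its literal wording, an event of uncertain cause is not counted. The rationale for that wording suggests the reverse was meant, and the recorded causality scale cannot resolve the difference. The count decides whether a dose is declared to exceed the MTD.

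The size cannot be derived from the documents. At a true rate of 50%, the chance of declaring the dose tolerable moves from 10.9% to 16.4%, 27.4% or 53.4% as the counted share falls from 100% to 90%, 75% or 50%. Those shares are assumptions, applied at subject level across both limbs. The finding does not extend to the hematologic limb, and it does not say which classification is clinically right.

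**What to change.** 1. The sponsor's clinical team should reconcile the sentence in the Synopsis, Protocol 9.1.1 and SAP 3.1.1 with its intended purpose, so that events of uncertain cause are classified deliberately and in the same way in every cohort. No particular clinical rule is proposed here.

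2. At each cohort review (SAP 7.1), give the SMC two numbers per dose level: the DLT count as defined, and the number of subjects with grade 3 or higher non-hematologic events, after the listed exceptions, that were not counted only because the cause was uncertain.

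3. Report the same two numbers in SAP 9.6.1.1. That section alone is not enough, because the SAP's tables serve the final study report and would not inform escalation.

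The cost is one sentence in three places and one extra row in the SMC display and the DLT table. The downside is that the displayed toxicity may look less favourable.
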